7.10 Epworth Sleepiness Scale[®]

The ESS[®] is a validated questionnaire designed to provide a subjective measure of daytime sleepiness. The ESS[®] consists of eight situations on chances of dozing; each situation is evaluated with a score that ranges from 0 (never dozing) to 3 (high chance of dozing). The eight items will be summed into a total score of daytime sleepiness.

The change from baseline (baseline as defined in Section 11.4) to Visit 3 (Week 14), Visit 4 (Week 27), Visit 5 (Week 40) and end of the run-out period Visit 6 (Week 41) in ESS[®] total score will be summarized. Observed values will also be summarized.

The number and percentage of subjects meeting the criteria defined below will be tabulated:

- ESS[®] total score > 16 at last value before start of treatment in the extension (it corresponds to last value before start of treatment collected on Day 1 of extension study) or in the confirmatory study), Visit 3 (Week 14), Visit 4 (Week 27), Visit 5 (Week 40) and end of the run-out period (Visit 6, Week 41).

- ESS[®] total score > 4 points increase from previous visit at Visit 3 (Week 14), Visit 4 (Week 27), Visit 5 (Week 40) and end of the run-out period (Visit 6, Week 41).

7.11 Subgroup analysis of safety variables

Summaries of TEAEs occurring (i.e., that started or worsened) during the double-blind study period [see Section 12.3] by SOC and PT will be performed on the following subgroups:

Age at screening of confirmatory study	< 65, ≥ 65 years and <75; ≥75
BMI at screening of confirmatory study	< 25, 25–30, > 30 kg/m ²
Sex	Male, female
Race	White, Black or African American, Other*

* The 'Other' category will not be considered for subgroup analyses due to the mix of races and small number of subjects limiting the ability (i.e., low power) to detect differences between treatment groups. 'Other' includes: American Indian or Alaska Native, Native Hawaiian or other Pacific Islander, Asian and Other (Entry for multiple races was to be reported under category 'Other'. Similarly, 'Not permitted as per legislation/regulation' was to be also grouped within this category 'Other').

8 PHARMACOKINETIC VARIABLES AND ANALYSES

Pharmacokinetic data, i.e., plasma concentrations of ACT-541468 (collected at the discretion of the investigator) will only be listed.

9 GENERAL STATISTICAL METHODOLOGY

9.1 General rules for data presentations

Data are listed and summarized as described below.

The tables for ID-078A303 will use the following header structure (label and order):

ACT-541468 10 mg N = xxx	ACT-541468 25 mg N = xxx	ACT-541468 50 mg N = xxx	Placebo N = xxx	Ex-placebo/ACT-541468 25 mg N = xxx
---	---	---	----------------------------------	--

- *ACT-541468 10 mg*: subjects continuing in the extension trial at the same dose level of 10 mg
- *ACT-541468 25 mg*: subjects continuing in the extension trial at the same dose level of 25 mg
- *ACT-541468 50 mg*: subjects continuing in the extension trial at the same dose level of 50 mg

- *Placebo*: subjects continuing in the extension trial assigned to placebo arm
- *Ex-placebo/ACT-541468 25 mg*: subjects continuing in the extension trial that switch from placebo to 25 mg

Where N indicates the total number randomized or treated appropriate to the analysis set in the corresponding treatment group, unless otherwise specified.

All listings will be sorted by randomized treatment or actual treatment received (appropriate to the analysis set), country, subject number (ascending) and, when appropriate, by visit / date of assessment (ascending).

Listings based on the ENR Set will present a treatment group label “Subject not randomized” for subjects who were not randomized and will be listed after the subjects who were randomized.

Unless noted otherwise, the following descriptive statistics will be used to summarize data: number and percentage of subjects for categorical variables or descriptive statistics (number of non-missing values, mean, standard deviation, median, Q1, Q3, minimum, maximum) for continuous variables.

10 INTERIM ANALYSES

This study includes an IDMC and ISB that will assess safety of ACT-541468 on a regular basis as per IDMC and ISB charters, respectively.

Safety and efficacy data supporting the review by IDMC will be provided by Idorsia for the part of analyses that are blinded and by an ISAC for the unblinded part.

An interim analysis was introduced as part of amendment protocol Version 3, dated 17 February 2020, to support global regulatory filings.

The interim analysis will be conducted when all subjects who did not prematurely discontinue study treatment have reached Visit 3.

A second interim analysis may be performed to fulfil the FDA requirement to submit updated safety data 120 days after NDA submission from ongoing studies, in case the study has not been completed by that time.

To maintain the integrity of the study after the interim analysis, participating subjects as well as investigators will remain blinded for the entire duration of the study. The sponsor personnel involved in data collection and medical monitoring of the study will also remain blinded until the end of the study.

The interim analysis will be based upon a snapshot of the clinical trial database and will include all clean safety and efficacy data as of approximately end of July (a cut-off date

will be fixed to ensure all subject data up to and including Visit 3 are included). All visits and assessments that have been done before and on this cut-off date will be considered for the interim analysis. All analyses described in this SAP will be performed for the interim analysis.

SDTM dataset will be based on the snapshot of the clinical database and may include data beyond the cut-off date. Then, ADaM datasets will be produced including only data up to the date of the interim cut-off.

No adjustment for multiple testing is required as no formal interim analysis will be performed for determining whether to stop (or modify) the study (i.e., no hypothesis testing will be conducted ad interim).

11 GENERAL DEFINITIONS AND DERIVATIONS

11.1 Treatment start and end dates

Unless noted otherwise, treatment start and end dates mentioned throughout this document are in reference to the treatment received in the extension study.

Double-blind study treatment start or end date is the earliest or latest, respectively, date of dose intake recorded on the 'Study Double-Blind Treatment Log' page. Double-blind study treatment start or end date of the confirmatory study is the earliest or latest, respectively, date of dose intake recorded on the 'Study Double-Blind Treatment Log' page of either study ID-078A301 or study ID-078A302.

Run-out single-blind placebo treatment start and end date is the earliest and latest date of dose intake recorded on the 'Study Single-Blind (Run-Out) Treatment Log' page.

11.2 Study periods

The enrollment period is defined as the time from the informed consent date until one day before double-blind study treatment start date.

The double-blind study period is defined as the time from the day of double-blind study treatment start until the day of EODBT (Visit 5) or for those who prematurely discontinued double-blind study treatment (i.e., those without an EODBT date), until one day after double-blind study treatment end date (if the treatment is taken before midnight), or the day of double-blind study treatment end date (if the treatment is taken after midnight). Time of treatment intake between 00:00 and 11:59 is considered as 'after midnight', while a time between 12:00 and 23:59 is considered as 'before midnight'. For any missing or incomplete time, it is presumed that the treatment was taken before midnight. For subjects lost to follow-up, the EOS date will be used as the end of DB study treatment. For subjects who complete double-blind study treatment with an interruption before continuing the run-out single-blind placebo treatment, the end of double-blind study period is the run-out

single-blind placebo treatment start date – 1 day. For subjects who prematurely discontinue treatment, the safety data (laboratory tests, ECG and vital signs) assessment up to 7 days after last drug intake are considered in the definition of double-blind study period [see Section 7.1].

For those subjects in the TWS, the treatment withdrawal period (or the run-out period) is defined as the time from one day after the end of the double-blind study period to the latter of seven days after the end of the double-blind study period or Visit 6 date. If the latter of the two dates falls after the EOS date, then the EOS date will be used.

The safety follow-up period is defined as the time from one day after the end of the treatment withdrawal period for those starting the treatment withdrawal period (i.e., subjects in the TWS) until the EOS date; or from one day after the end of double-blind study period for those not starting the treatment withdrawal period until the EOS date.

11.3 Treatment day and study day

The treatment day for an assessment or event will be calculated using the double-blind study treatment start date as reference.

For assessments/events occurring on or after the start date of double-blind study treatment, the treatment day will be positive and will be calculated as:

Treatment day (days) = Date of assessment/event – Start date of double-blind study treatment + 1 day.

The first day of double-blind study treatment is Treatment Day 1.

For all assessment/events occurring prior to the start date of double-blind study treatment, the treatment day will be negative and calculated as:

Treatment day (days) = Date of assessment/event – Start date of double-blind study treatment.

The study day for an assessment or event will be calculated using the randomization date as reference.

For assessments/events occurring on or after the randomization date, the study day will be positive and calculated as:

Study day (days) = Date of assessment/event – randomization date + 1 day.

The day of randomization date is Study Day 1.

For all assessment/events occurring prior to the randomization date, study day will be negative and calculated as:

Study day (days) = Date of assessment/event – randomization date.

Treatment day and/or study day will be displayed in the data listings as appropriate.

11.4 Baseline

Unless otherwise defined in the specific analysis section, baseline is defined as follows:

1. For subjects entering ID-078A303 and assigned to the same treatment arm as that of the confirmatory studies (ACT-541468 10 mg, 25 mg, or 50 mg, or placebo), baseline is the last non-missing assessment performed or value measured before or on the day of first dose of double-blind study treatment in the confirmatory study.
2. For subjects entering ID-078A303 who received placebo in the confirmatory studies and who are randomized (switched) to 25 mg of ACT-541468 in the extension study, baseline is the last non-missing assessment performed or value measured before or on the day of first dose of double-blind study treatment in the extension study. This could be either data collected at Visit 1 of the extension study or collected in the confirmatory study. An assessment taken on the day of the double-blind study treatment start date is considered a baseline assessment and is not considered a post-baseline assessment in the double-blind study period.

Subjects with no data on a particular parameter before the first treatment administration will have a missing baseline (and change from baseline) for this parameter.

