7.3 Laboratory tests

Laboratory analyses are based on data received from the central laboratory. Laboratory data will be converted into SI units. Unless noted otherwise, summaries and listings will include scheduled, re-test and unscheduled assessments.

Descriptive summary statistics for each scheduled visit (re-test excluded) will be provided for observed values and change from baseline (baseline as defined in Section 11.4) in both hematology and blood chemistry laboratory parameters.

The change from baseline to the last value (re-test and unscheduled assessments excluded) in the double-blind study period for hematology and blood chemistry parameters will be summarized.

Marked laboratory abnormalities are defined in Table 4. The number and percentage of subjects with marked laboratory abnormalities during double-blind study treatment will be tabulated. In the event of multiple occurrences, a subject will be counted only once but may be reported in more than one marked laboratory abnormality criterion of a given parameter.

Percentages will be based on the number of subjects at risk, i.e., those having at least one post-baseline value for a given parameter.

Shift from baseline to worst value post-baseline based on laboratory normal ranges will be provided for the following laboratory parameters:

- Liver enzymes: ALT, AST, gamma-glutamyl transpeptidase and TBIL.
- Thyroid hormones: thyroid-stimulating hormone, free triiodothyronine and free thyroxine.
- Lipids: total cholesterol and triglycerides.
- Hematology: leucocytes, neutrophils, lymphocytes, and eosinophils.

All laboratory data for subjects with at least one marked laboratory abnormality during double-blind study treatment will be listed. Any local laboratory data collected will be listed separately.

Table 4 **Marked abnormalities in laboratory parameters for reporting**

Laboratory parameter	Criteria for marked laboratory abnormalities
Hematology (SI unit)	
Hemoglobin (g/L)	< 100 < 80 > 20 above ULN or > 20 above baseline if baseline > ULN > 40 above ULN or > 40 above baseline if baseline > ULN
Hematocrit (%)	< 32% (Male); < 28% (Female) < 20% > 60% (Male); > 55% (Female)

Laboratory parameter	Criteria for marked laboratory abnormalities
	> 65%
Platelets (10 ⁹ /L)	< 75 < 50 > 600 > 999
Leucocytes (10 ⁹ /L)	< 3.0 < 2.0 > 20.0 > 100.0
Neutrophils (10 ⁹ /L)	< 1.5 < 1.0
Eosinophils (10 ⁹ /L)	> 5.0
Eosinophils (%)	> 5%
Lymphocytes (10 ⁹ /L)	< 0.8 < 0.5 > 4.0 > 20.0
Reticulocyte (%)	> 2.5%

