7.4 Electrocardiography

Unless noted otherwise, ECG summaries and listings will include scheduled, re-test and unscheduled assessments.

Descriptive summary statistics for each scheduled visit (re-test excluded) will be provided for observed values and change from baseline (baseline as defined in Section 11.4) to Visit 3 (Week 14), Visit 4 (Week 27), Visit 5 (Week 40) and Visit 6 (Week 41) in ECG parameters (QT corrected according to Fridericia's formula, QT corrected according to Bazett's formula, heart rate, PR, and QRS).

Marked ECG abnormalities are defined in Table 5. The following summaries will be provided for each ECG parameter:

- Number and percentage of subjects having a marked ECG abnormality during the double-blind study period,
- Number and percentage of subjects having a marked ECG abnormality during the treatment withdrawal period (based on the TWS).

For the summaries above, percentages will be based on the number of subjects at risk: those having at least one post-baseline value in the study period under consideration per ECG parameter for criteria based on post-baseline values only, or those having a baseline value and at least one post-baseline value in the study period under consideration per ECG parameter for criteria based on change from baseline. For non-mutually exclusive criteria (i.e., HR < 45 bpm and < 50 bpm), a subject will be counted only once in the event of multiple occurrences but may be reported in more than one marked ECG abnormality criterion of a given parameter. For mutually exclusive criteria (e.g., HR and QTc), only the subject's worst post-baseline value (or worst change from baseline value) will be counted.

ECG findings during the double-blind study period and during the treatment withdrawal period (based on the TWS) will be summarized separately and listed.

ECG abnormality categories and findings will be sorted by descending frequency, first in the ACT-541468 50 mg dose level, then in the ACT-541468 25 mg dose level, then in the ACT-541468 10 mg, then in the placebo treatment group, and finally in the ex-placebo/ACT-541468 25 mg. After this sorting, ECG abnormality categories will be presented in alphabetical order with ECG finding sorted within ECG abnormality category in alphabetical order.

All ECG values for subjects with at least one marked ECG abnormality during double-blind study period or during the treatment withdrawal period will be listed.

Table 5 **Marked abnormalities in ECG parameters**

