7.9 Columbia Suicide Severity Rating Scale[®]

The C-SSRS[®] is an instrument that evaluates suicidal ideation and behaviors.

The C-SSRS[®] outcome categories are provided below. Each category has a binary response (yes/no) and are numbered and ordered for convenience.

1. Wish to be Dead
2. Non-specific Active Suicidal Thoughts
3. Active Suicidal Ideation with Any Methods (Not Plan) without Intent to Act
4. Active Suicidal Ideation with Some Intent to Act, without Specific Plan
5. Active Suicidal Ideation with Specific Plan and Intent
6. Preparatory Acts or Behavior
7. Aborted Attempt
8. Interrupted Attempt
9. Actual Attempt (Non-Fatal)
10. Completed Suicide

Self-injurious behavior without suicidal intent is also a C-SSRS[®] outcome (although not suicide-related) and has a binary response (yes/no).

Categories 1–5 relate to suicidal ideation and a score of 0 is assigned if no suicidal ideation is present. Categories 6–10 relate to suicidal behavior.

Based on the C-SSRS[®], the number and percentage of subjects with suicidal ideation by category, suicidal behavior by category, suicidal ideation or behavior and/or self-injurious behavior without suicidal intent, 1) during the double-blind study period and 2) during the treatment withdrawal period (based on TWS) will be tabulated separately. Percentages will be based on the number of subjects with at least one post-baseline C-SSRS[®] assessment, in the corresponding period. The assessment will be assigned to a study period based on a scheduled visit as follows: V1 (Day 1) = not assigned any study period; V3 (Week 14), V4 (Week 27) and V5 (Week 40) = double-blind study period; V6 (Week 41) = Treatment withdrawal (or Run-out) period.

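### As printed, SAP 11.4 stops a first-dose-day value from counting as post-baseline only in the ex-placebo/25 mg arm, so any Visit 1 ECG or laboratory value could count in the four continuing arms alone

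*SAP*

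**What the plan says.** SAP Section 11.4 gives two baseline definitions.

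- **Item 1** covers subjects who stay on their confirmatory-study arm, whether placebo or one of the three doses (10, 25 and 50 mg). Its rule reads "baseline is the last non-missing assessment performed or value measured before or on the day of first dose of double-blind study treatment in the confirmatory" (that is, ID-078A301 or ID-078A302).
- **Item 2** covers subjects switched from placebo to 25 mg and takes the last value up to and including the day of the first extension dose. It adds: "This could be either data collected at Visit 1 of the extension study or collected in the confirmatory study". Its final sentence says that a value taken on the start date is "considered a baseline assessment and is not considered a post-baseline assessment in the double-blind study period".

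Section 11.1 fixes which start date is meant: unless noted otherwise, "treatment start and end dates mentioned throughout this document are in reference to the treatment received in the extension study".

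Section 11.2 sets the period by calendar day, with no split before and after the dose: "The double-blind study period is defined as the time from the day of double-blind study treatment start until the day of EODBT (Visit 5". Section 11.5 treats anything after baseline and up to end of study as post-baseline.

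Three outputs depend on these definitions:

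- Section 7.4 tabulates "Number and percentage of subjects having a marked ECG abnormality during the double-blind study period" and summarises ECG findings for the same period. Scheduled, re-test and unscheduled recordings are all included.
- Section 7.3 states: "Shift from baseline to worst value post-baseline based on laboratory normal ranges will be provided". No study period is named.
- Section 7.9, for the C-SSRS only, has its own rule for every arm: "V1 (Day 1) = not assigned any study period".

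**The concern.** Sections 7.3 and 7.4 have no counterpart to the C-SSRS rule, so the only sentence keeping a first-dose-day ECG or laboratory value out of the post-baseline counts is the one in item 2 of Section 11.4. Read where it stands, it protects one arm of five.

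Long-term safety is the primary objective, and Section 9.1 prints the five arms side by side. By Section 2, the only allocation randomised within this study is former placebo subjects to placebo or 25 mg, 1:1. Those two arms would be counted under different rules. Continuing placebo would have one extra chance to be flagged, which would work against seeing an ECG or laboratory effect of 25 mg.

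There is a second consequence in the continuing active arms. Subjects enter the extension after the confirmatory run-out, so a pre-dose Visit 1 value is off drug. It would nevertheless be reported as arising in the double-blind period.

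**Working it through.** The plan states no figure on this point. The check is a rule trace followed by an illustration of size.

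**Rule trace: pre-dose ECG on the date of the first extension dose**

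| Step | Continuing arms (10, 25, 50 mg, placebo) | Ex-placebo/25 mg |
|---|---|---|
| Baseline (11.4) | Fixed in the confirmatory study | Can be this value |
| After baseline? (11.5) | Yes | No |
| Inside the double-blind period? (11.2) | Yes, the whole day is included | Yes by date |
| Barred from post-baseline? (11.4) | No sentence in item 1 | Yes, last sentence of item 2 |
| Can enter the double-blind ECG tables (7.4)? | Yes | No |

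**Which outputs are reached**

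- *Marked ECG abnormalities and ECG findings*: reached, because both are tied to the double-blind study period. If the first dose is dated the day after Visit 1, for instance because it was taken after midnight, Visit 1 falls in the enrollment period in every arm and the asymmetry disappears.
- *Laboratory shift to worst value*: reached. No period is named, so Section 11.5 alone decides, even when the first dose is dated a day later.
- *Marked laboratory abnormalities and elevated liver parameters*: less clearly reached. Section 7.3 counts these while on double-blind treatment, and a pre-dose value is arguably not on treatment.

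**Size, as an illustration only**

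Assumptions: an ECG exists at Visit 1 on the first-dose date; Visits 3, 4 and 5 are the scheduled double-blind looks; there is no drug effect; the chance p of crossing the threshold is the same at each look. The continuing arms then have k = 4 looks and ex-placebo/25 mg has k = 3.

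Independent looks: P(flagged) = 1 − (1 − p)^k. With p = 2%:

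- k = 4: 1 − 0.98⁴ = 7.76%
- k = 3: 1 − 0.98³ = 5.88%

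Correlated looks: each look is a standard normal crossing c = Φ⁻¹(1 − p), with common correlation ρ between looks, so P(flagged) = 1 − ∫ φ(z) Φ((c − √ρ·z)/√(1 − ρ))^k dz. The last column is (P₄ − P₃)/P₄.

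| ρ (p = 2%) | 4 looks | 3 looks | Flagged only because of the extra look |
|---|---|---|---|
| 0 | 7.8% | 5.9% | 24% |
| 0.5 | 6.4% | 5.1% | 20% |
| 0.8 | 4.7% | 4.0% | 14% |
| 0.95 | 3.2% | 3.0% | 8% |
| 1 | 2.0% | 2.0% | 0% |

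At the interim analysis, a subject who has only reached Visit 3 has two looks against one. With p = 2% this gives 1 − 0.98² = 4.0% versus 2.0% for independent looks, and 2.6% versus 2.0% at ρ = 0.95.

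If no Visit 1 value exists, or the exclusion is applied to all arms, every arm has the same looks and the gap is zero.

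**The case against.** **The extra look may not exist.** The available protocol document is the COVID-19 addendum, and neither it nor the SAP contains a visit schedule showing an ECG or laboratory sample at extension Visit 1. Section 7.4 names Visits 3 to 6 for ECG change from baseline. The reference to Visit 1 data in Section 11.4 is a generic baseline rule for every parameter. The instruments that the SAP shows on Day 1 are the C-SSRS and the ESS, which may be the only reason the C-SSRS has its own rule. Section 1 also limits reporting to extension data apart from some baseline and subject-characteristics data, so transition tests belonging to the confirmatory study would not be counted here. This stands, and it makes the consequence conditional. It does not repair the text: Section 7.4 also takes unscheduled and re-test ECGs, so any recording on that date is caught.

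**The exclusion sentence names no arm.** It can be read as covering everyone. But it would then call a continuing subject's Visit 1 value a baseline assessment, against item 1, which fixes that baseline in the confirmatory study. One reading gives unequal rules and the other contradicts a definition, so the wording needs correcting either way.

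**The effect is narrow and may be small.** The four continuing arms share one rule. The tables are descriptive, and the ex-placebo baseline already differs by design. Independent looks are the least plausible case for subject-specific measures such as PR or QRS. All of this stands.

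A reader might infer that the marked-abnormality tables are certain to understate an ECG or laboratory effect of 25 mg. The documents do not support that: the Visit 1 value is not shown to exist, the sentence has a second reading, and the marked-laboratory and liver tables use a different time reference.

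**Conclusion.** The drafting gap is real. Taken as printed, Sections 11.2, 11.4 and 11.5 let a first-dose-day ECG count as a double-blind post-baseline value in four arms and not in the fifth, and let a Visit 1 laboratory value enter the worst-value shift in the same four arms.

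The consequence depends on such values existing and on the exclusion being programmed for item 2 only. If both hold, contrasts with ex-placebo/25 mg have unequal looks, and off-drug values appear as double-blind in the continuing active arms. At the assumed 2% per look the difference in subjects flagged runs from about 1.9 percentage points with independent looks (7.76 − 5.88) to about 0.3 at correlation 0.95, and to nothing without a Visit 1 value. The 2% and the correlations are assumptions, not trial data. Comparisons among the continuing doses and continuing placebo keep equal looks throughout.

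It is worth correcting because it touches the one randomised comparison in the study and the correction costs almost nothing.

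**What to change.** Place one sentence outside the numbered items of SAP Section 11.4, in place of the last sentence of item 2:

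*For all subjects, a laboratory or ECG assessment taken before the first extension dose, including on the day of first dose, is assigned to no study period and is not a post-baseline value for any double-blind-period or worst-value summary.*

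Leave both baseline definitions unchanged, so that a Visit 1 value can still be the baseline for ex-placebo/25 mg subjects, and keep all such values in the listings. Using one period term in Sections 7.3 and 7.4 would also settle the doubt over the marked-laboratory and liver tables. Vital signs need no such rule, because Section 7.5 summarises them by scheduled visit and has no worst-value or marked-abnormality table.

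The cost is one sentence and a date filter in the analysis datasets, with no new data. The downside is that an abnormality seen only at Visit 1 in a continuing arm leaves these tables and appears only in the listings. If no ECG or laboratory value is taken at Visit 1, the sentence changes nothing for scheduled data.
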